SAP Version	Approval Date	Changes	Rationale
1.0	04-Feb-2021	Not Applicable	Original version
2.0	20-Apr-2021	In the case of an early primary database lock prior to the last enrolled participant reaching the end of treatment (EOT), analyses for the endpoints up to Week 12 use ITT-Week-12 population and beyond Week 12 use the ITT-Week-24 population. Add ITT-Week-12 and ITT-Week-24 populations In the case of an early primary database lock prior to the last enrolled participant reaching EOT, the additional exposure-adjusted adverse event incidence rate tables will provide the number of patients with at least 1 event per 100 patient-years.	EFC16459 and EFC16460 are 2 pivotal Phase 3 studies of identical design with EFC16460 data that will be available prior to EFC16459 data. Using data from EFC16460, the sample size calculation will be revisited aiming for a statistical power of at least 90% at an alpha level of 0.05 for the primary and key secondary endpoints in the respective analysis populations and the database lock will be performed when the number of participants based on this revised sample size are expected to have reached their Week 24 visit. This revised estimation may result in database lock occurring earlier than last participant reaching the end of treatment. At a minimum, this will include at least 135 participants having Week 24 pertinent data included at the time of database lock. Based on the timing of the availability of the EFC16460 results, and to ensure a minimum of 135 participants have the opportunity to reach the Week 24 endpoint, the randomization cut-off dates have been assessed as 22 March 2021 for Week 24 and 14 June 2021 for Week 12.
		Remove Appendix 7 in Section 5.7	A separate medication/procedure adjudication document for details

SAP Version	Approval Date	Changes	Rationale
3.0	08-Aug-2021	
Remove all modifications specific to early database lock previously made in SAP version 2 to align with Protocol Amendment 2 including discussion on the criteria used to perform early database lock and reference to the ITT-Week 12 and ITT-Week 24 populations.
 
Retain additional exposure-adjusted adverse event incidence rate tables that will provide the number of patients with at least 1 event per 100 patient-years previously made in SAP version 2.
 
Retain “Keratitis FDA” to other AE groupings previously made in SAP version 2
 
Add objective “To demonstrate efficacy of dupilumab on both itch as well as skin lesions within the same participant” and multicomponent endpoint (Proportion of participants with both an improvement (reduction) in WI-NRS by ≥ 4 from baseline to Week 24 and an IGA PN-S 0 or 1 score at Week 24) as a key secondary endpoint for the US and US reference countries hierarchy.
 
Add supplementary analysis (tipping point analyses) for primary and key secondary endpoints
	Based on a health authority's feedback on Protocol Amendment 2, the Sponsor made the decision to complete the study as originally planned instead of resizing the study based on the results of EFC16460
		Add subgroup analyses for key secondary endpoints.	As requested by a health authority to include exposure-adjusted incidence rate and patient years in the summaries for TEAEs and AESIs.
		Add subgroup analyses for participants who have been impacted (or not) by COVID-19	For consistency with other dupilumab studies
		Modify hierarchical order for multiplicity procedure for US and US reference countries	To add this multicomponent endpoint as another measure of treatment success based on feedback from a health authority.
		Add as-observed plus multiple imputation supplementary analysis for the secondary endpoint (percent change from baseline in WI-NRS at Week 24)	This additional supplementary analysis was recommended by a health authority to assess whether the estimate, and the inference thereof, was robust to departure from the strategies used in primary analysis for handling intercurrent events and missing data.
			To evaluate whether the treatment effect is consistent across pre-specified sub-groups on the key secondary endpoints in addition to the primary endpoint.
			To address a health authority's request to assess the impact of the treatment effect by COVID-19.
			To include the multicomponent endpoint in the hierarchy to address the health authority's feedback requesting assessment of this endpoint as another measure of treatment success.
			To explore the robustness of the estimate, and the inference thereof, with a different strategy for handling intercurrent events and missing data

SAP Version	Approval Date	Changes	Rationale
		Remove "selected" in the text including "selected prohibited and/or rescue medication"	Since a participant who takes any protocol specified prohibited medications/procedures and/or rescue medications is considered as a non-responder after medical adjudication/confirmation conducted in a blinded fashion, use of the word "selected" may be confusing.
		Add Appendix 7 back in Section 5.7	Add this medication/procedure adjudication algorithm back as it was inadvertently removed in SAP Version 2.
4.0	11-Nov-2021	
To promote the "proportion of participants with improvement (reduction) in worst-itch numeric rating scale (WI-NRS) by ≥ 4 from baseline to Week 24 as primary endpoint and to move the "proportion of participants with improvement (reduction) in WI-NRS by ≥ 4 from baseline to Week 12" to a secondary endpoint
 
To update hierarchical order in Section 4.6 by removing "Proportion of participants with improvement (reduction) in WI-NRS by ≥ 4 from baseline to Week 12", "Proportion of participants with IGA PN-S 0 or 1 score at Week 12" and "Change from baseline in Sleep-NRS to Week 24"
	
Based on the data from EFC16460, the treatment effect of dupilumab continued to improve over time through Week 24. Therefore, the Sponsor proposes to assess the proportion of participants with improvement (reduction) in WI-NRS by ≥ 4 at Week 24, which represents the effect more accurately and synchronizes the primary itch assessment with the primary lesion assessment. This is consistent with primary endpoint change in Protocol Amendment 3.
 
Updated power calculations performed using data from study EFC16460 showed low power for demonstrating statistical significance for each of these three endpoints. Accordingly, the hierarchical order was revised to remove these endpoints.

The first participant was randomized on 2020-01-02.

1 INTRODUCTION

1.1 STUDY DESIGN

This study is a multi-center, 24-week treatment, parallel group, double-blind, randomized, placebo-controlled study to evaluate the use of dupilumab in participants with prurigo nodularis (PN) inadequately controlled on topical prescription therapies or when those therapies are not advisable. The study will assess the effect of dupilumab on itch improvement as well as its effect on PN lesions, on participants' health-related quality of life (HRQoL), anxiety and depression, sleep quality, skin pain, and overall health status.

After 2-4 weeks of screening, participants will be centrally randomized using a permuted block randomization schedule via Interactive Voice Response System/Interactive Web Response System (IVRS/IWRS) in a 1:1 randomization ratio to dupilumab 300 mg q2w or matching placebo. Randomization will be stratified by documented history of atopy (atopic or non-atopic), stable use of topical corticosteroids (TCS)/topical calcineurin inhibitors (TCI) (yes or no), and country/territory code.

A total of approximately 150 participants will be randomized to two treatment arms (75 participants/arm). The number of participants with active mild AD upon study entry will represent up to 10% of the atopic participants. Both the atopic and the non-atopic PN populations will each be capped at 60% of the total enrolled population.

The study duration consists of the following periods:

- Screening period (2-4 weeks)
- Randomized IMP intervention period (24 weeks)
- Follow-up period (12 weeks).

1.2 OBJECTIVE AND ENDPOINTS

Table 2 - Objectives and endpoints

Objectives	Endpoints
Primary	

• To demonstrate the efficacy of dupilumab on itch response in participants with PN, inadequately controlled on topical prescription therapies or when those therapies are not advisable.	
• Proportion of participants with improvement (reduction) in worst-itch numeric rating scale (WI-NRS) by ≥ 4 from baseline to Week 24.
Secondary	

• To demonstrate the efficacy of dupilumab on additional itch endpoints in participants with PN, inadequately controlled on topical prescription therapies or when those therapies are not advisable.	
• Time to onset of effect on pruritus as measured by proportion of participants with an improvement (reduction) in WI-NRS by ≥ 4 from baseline during the 24-week treatment period.• Change from baseline in WI-NRS at Week 24.• Change from baseline in WI-NRS at Week 12.

Objectives	Endpoints
	
 Percent change from baseline in WI-NRS at Week 24. Percent change from baseline in WI-NRS at Week 12. Proportion of participants with improvement (reduction) in WI-NRS by ≥ 4 from baseline to Week 12. Percent change from baseline in WI-NRS at Week 4. Percent change from baseline in WI-NRS at Week 2. Percent change from baseline in WI-NRS over time until Week 24. Proportion of participants with WI-NRS reduction ≥ 4 at Week 4. Proportion of participants with WI-NRS reduction ≥ 4 over time until Week 24^a. Onset of action in change from baseline in WI-NRS (first $p < 0.05$ difference from placebo in the daily WI-NRS that remains significant at subsequent measurements) until Week 12^b.

 To demonstrate efficacy of dupilumab on skin lesions of PN. 	
 Proportion of participants with Investigator's Global Assessment 0 or 1 score for PN-Stage (IGA PN-S) at Week 24 [Key secondary endpoint]. Proportion of participants with IGA PN-S 0 or 1 score at Week 12. Proportion of participants with IGA PN-S 0 or 1 score at Week 8^c. Proportion of participants with IGA PN-S 0 or 1 score at Week 4^c. Change from baseline in IGA PN-S score at Week 24. Change from baseline in IGA PN-S score at Week 12. Change from baseline in IGA PN-S score at Week 8. Change from baseline in IGA PN-S score at Week 4. Proportion of participants with Investigator's Global Assessment 0 or 1 score for PN-Activity (IGA PN-A) at Week 24. Proportion of participants with IGA PN-A 0 or 1 score at Week 12. Proportion of participants with IGA PN-A 0 or 1 score at Week 8. Proportion of participants with IGA PN-A 0 or 1 score at Week 4.

 To demonstrate efficacy of dupilumab on both itch as well as skin lesions within the same participant 	
 Proportion of participants with both an improvement (reduction) in WI-NRS by ≥ 4 from baseline to Week 24 and an IGA PN-S 0 or 1 score at Week 24 (key secondary endpoint for US and US reference countries only).

 To demonstrate the improvement in health-related quality of life (HRQoL). 	
 Change from baseline in HRQoL, as measured by Dermatology Life Quality Index (DLQI) to Week 24. Change from baseline in HRQoL, as measured by DLQI to Week 12.

 To evaluate safety outcome measures. 	
 Percentage of participants experiencing treatment-emergent adverse events (TEAEs) or serious adverse events (SAEs) from baseline through Week 24.

Objectives	Endpoints

 To evaluate immunogenicity of dupilumab. 	
 Incidence of treatment-emergent antidrug antibodies (ADA) against dupilumab over time.
Tertiary/exploratory	

 To demonstrate a reduction in the use of rescue medication and systemic immunosuppressant To evaluate exploratory outcome measures 	
 Use of high potency or superpotent TCS rescue medication through Week 24 Use of systemic immunosuppressants through Week 24, constituting treatment failure Change from baseline in Hospital Anxiety and Depression Scale (HADS) total score to Week 24. Change from baseline in EQ5D-5L to Week 24. Change from baseline in skin Pain numeric rating scale (NRS) to Week 4, Week 8, Week 12, and Week 24, respectively. Change from baseline in Sleep NRS to Week 4, Week 8, Week 12, and Week 24, respectively. Missed school/work days through Week 24. Incidence of skin-infection TEAEs (excluding herpetic infections) through Week 24.

 To evaluate the efficacy of dupilumab on skin lesions using a modified PAS 5-item questionnaire To evaluate the efficacy of dupilumab on other PN endpoints 	
 Proportion of participants who achieve $\geq 75\%$ healed lesions from Prurigo Activity Score (PAS) at Week 4, Week 8, Week 12, and Week 24, respectively. Change from baseline in exact number of lesions in representative area (as determined from PAS) at Week 4, Week 8, Week 12, and Week 24, respectively. Change from baseline in Participant Global Impression of Severity (PGIS) of PN to Week 4, Week 8, Week 12, and Week 24, respectively. Participant Global Impression of Change (PGIC) of PN at Week 4, Week 8, Week 12, and Week 24, respectively.
PK	

 To evaluate pharmacokinetic (PK) and pharmacodynamic (PD) outcome measures 	
 Serum functional dupilumab concentrations and PK profile. Pharmacodynamic response for selected biomarkers (total IgE).

- a The early onset for significant change in the proportion of responders with WI-NRS reduction ≥ 4 between dupilumab and placebo will be claimed at Week xx if the p-value for Week xx is <0.05 and the remaining timepoints also have nominal p-value ≤ 0.05 until Week 12.
- b The early onset for significant change in WI-NRS from baseline between dupilumab and placebo will be claimed at Week xx if the p-value for Week xx is <0.05 and the remaining timepoints also have nominal p-value ≤ 0.05 until Week 12.
- c The early onset for reaching IGA PN-S (0,1) between dupilumab and placebo will be claimed at Week xx if the p-value for Week xx is ≤ 0.05 and the remaining timepoints also have nominal p-value ≤ 0.05 until Week 12.

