1.3 SCHEDULE OF ACTIVITIES (SOA)

Procedure	Screening (2 to 4 weeks before Day 1)	Intervention period (Weeks)					Follow-up (12 weeks)	Notes
		0 (Day 1)	4	8	12	24		
Visit	1	2 ^a	3	4	5	6 ^b (EOT)	7 (EOS)	Visit window: ± 3 days for Visits 3, 4, 5, 6, and 7.
Screening and baseline								
Informed consent	X							Separate consent to be obtained for optional procedures (skin biopsy, DNA and RNA sampling, serum/plasma sampling for archival, and photography; HIV test if specific consent locally required).
Medical history	X							
Prior and concomitant medication	X	X	X	X	X	X	X	Concomitant medication will be collected throughout the study.
Demography	X							
Inclusion and exclusion criteria	X	X						
Hepatitis ^c , HIV serology, TB test	X							HBs Ag, HBs Ab, HBc Ab, HCV Ab, HIV screen (Anti-HIV-1 and HIV-2 antibodies), TB test (performed locally if required and results noted in the eCRF).
Randomization		X						
Study intervention^d								
Dispense or download e-diary	X	X	X	X	X	X	X	Device will be dispensed at Screening (including instructions for use). At EOS, the e-diary will be downloaded and returned to the site.
Participant e-diary training	X	X						
Call IVRS/IWRS	X	X	X	X	X	X	X	At screening visit, IVRS/IWRS will be called after medical history check.
IMP administration		X	X	X	X			IMP administration Q2W (± 3 days) from Week 0 until Week 22. Between visits, the participants will self-inject IMP at home or may choose to have injections administered at home by a caregiver or at the study site.

Procedure	Screening (2 to 4 weeks before Day 1)	Intervention period (Weeks)					Follow-up (12 weeks)	Notes
		0 (Day 1)	4	8	12	24		
Visit	1	2 ^a	3	4	5	6 ^b (EOT)	7 (EOS)	Visit window: \pm 3 days for Visits 3, 4, 5, 6, and 7.
Safety^d								
Physical examination	X	X				X	X	Including skin (full body skin exam), nasal cavities, eyes, ears, respiratory, cardiovascular, gastrointestinal, neurological, lymphatic, and musculoskeletal systems.
Vital signs	X	X	X	X	X	X	X	Including SBP and DBP (mmHg), pulse rate (beats per minute), body temperature (°C), and respiratory rate. Body weight will be recorded at Visits 1, 6, and 7 only. Height will be recorded at Visit 1 only.
12-lead ECG	X					X		Locally collected and read.

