9.4.2 Safety analyses

All safety analyses will be performed on the safety population. The summary of safety results will be presented by treatment group. The baseline value is defined generally as the last available value before randomization.

Table 7 - Safety analyses

Endpoint	Statistical analysis methods
Percentage of participants experiencing TEAEs or SAEs from baseline through Week 24	Adverse event incidence tables will present by SOC (sorted by internationally agreed order), and PT sorted in alphabetical order for each treatment group, the number (n) and percentage (%) of participants experiencing an AE. In addition, exposure-adjusted AE incidence rate tables will provide the number of patients with at least 1 event per 100 patient-years, presented by SOC and PT. Multiple occurrences of the same event in the same participant will be counted only once in the tables within a treatment phase. The denominator for computation of percentages is the safety population within each treatment group. Proportion of participants with at least one TEAE, treatment emergent SAE, TEAE leading to death, and TEAE leading to permanent treatment discontinuation will be tabulated by treatment group. In addition, TEAEs will be described according to maximum intensity and relation to the study intervention. Serious AEs and AEs leading to study discontinuation that occur outside the treatment-emergent period will be summarized separately.

AE: adverse event; PT: preferred term; SOC: system organ class; SAE: serious adverse event; TEAE: treatment-emergent adverse event.

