4 STATISTICAL ANALYSES

4.1 GENERAL CONSIDERATIONS

In general, continuous data will be summarized using the number of observations available, mean, standard deviation (SD), median, minimum, and maximum. Categorical and ordinal data will be summarized using the count and percentage of participants.

The baseline value of efficacy parameters is defined as the last available value before randomization and prior to the first dose of study medication unless below eDiary data (WI-NRS, skin Pain-NRS and Sleep-NRS) score or otherwise specified.

The baseline for weekly average WI-NRS (skin Pain-NRS and Sleep-NRS) score is defined as the average of daily non-missing scores obtained during the 7 days prior to randomization.

The baseline value of the other parameters is defined as the last available value prior to the first dose of investigational medicinal product (IMP) if the participant is treated, or the last available value up to randomization if the participant is not exposed to IMP.

Observation period

The observation period will be divided into 4 segments:

- The **pre-treatment period** is defined as the period up to first IMP administration.
- The **treatment-emergent (TE) period** is defined as the period from the first IMP administration to the last IMP administration + 98 days. The treatment-emergent period includes the following 2 periods:
 - The **on-treatment period** is defined as the period from the first IMP administration to the last administration of the IMP + 14 days
 - The **residual treatment period** is defined as the period from the end of the on-treatment period to the end of the treatment-emergent period.
- The **post-treatment period** is defined as the period from the end of the treatment-emergent period.

The on-study observation period is defined as the time from start of intervention until the end of the study defined as the status date collected on e-CRF page “Completion of End of Study”.

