4.7.2 Adverse events

General common rules for adverse events

All adverse events (AEs) will be coded to a lower-level term (LLT), preferred term (PT), high-level term (HLT), high-level group term (HLGT), and associated primary system organ class (SOC) using the Medical Dictionary for Regulatory Activities (MedDRA) version currently in effect at Sanofi at the time of database lock.

The AEs will be analyzed in the following 3 categories:

- Pre-treatment AEs: AEs that developed, worsened or became serious during the pre-treatment period.
- Treatment-emergent adverse events (TEAE)s: AEs that developed, worsened or became serious during the treatment-emergent period
- Post-treatment AEs: AEs that developed, worsened or became serious during the post-treatment period

Similarly, the deaths will be analyzed in the pre-treatment, treatment-emergent and post-treatment periods.

The primary focus of AE reporting will be on TEAEs. Pre-treatment and post-treatment AEs will be described separately.

An AE with incomplete or missing date/time of onset (occurrence, worsening, or becoming serious) will be classified as a TEAE unless there is definitive information to determine it is a pre-treatment or a post-treatment AE.

If the assessment of the relationship to IMP is missing for an AE, this AE will be assumed as related to IMP. If the severity is missing for 1 of the treatment-emergent occurrences of an AE, the severity will be imputed with the maximal severity of the other occurrences. If the severity is missing for all the occurrences, the severity will be left as missing.

Multiple occurrences of the same event in the same participant will be counted only once in the tables within a treatment phase.

The AE tables will be sorted as indicated in [Table 6](#).

Table 6 - Sorting of AE tables

AE presentation	Sorting rules
SOC, HLT, HLT and PT	By the internationally agreed SOC order and by alphabetic order of HLTs, HLTs and PTs.
SOC, HLT and PT	By the internationally agreed SOC order and by alphabetic order of HLTs and PTs.
SOC and PT	By the internationally agreed SOC order and decreasing frequency of PTs ^{a, b}
SMQ/CMQ and PT	By decreasing frequency of SMQs/CMQs and PTs ^a

AE presentation	Sorting rules
PT	By decreasing frequency of PTs ^a

^a Sorting will be based on the SAR231893 dupilumab group

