^b The table of all TEAEs presented by SOC and PT will define the presentation order for all other tables (eg, treatment-emergent SAE) presented by SOC and PT, unless otherwise specified.

Analysis of all adverse events

The overview of TEAE with the details below will be generated:

- Any TEAE
- Any severe TEAE
- Any treatment emergent SAE
- TEAE leading to death
- Any TEAE leading to permanent intervention discontinuation
- Any treatment emergent AESI
- Any treatment emergent other AE of interest grouping
- Any TEAE related to IMP

The AE summaries of [Table 7](#) will be generated with number (%) of participants experiencing at least one event.

Table 7 - Analyses of adverse events

Type of AE	MedDRA levels
All TEAE	Primary SOC, HLGT, HLT and PT
	Primary SOC and PT
	PT
	Primary and secondary SOC, HLGT, HLT and PT
Common TEAE ($\geq 2\%$ and 5% in any group)	Primary SOC and PT
TEAE related to IMP as per Investigator's judgment	Primary SOC, HLGT, HLT and PT
	Primary SOC and PT
TEAE by maximal intensity	Primary SOC and PT
Treatment emergent SAE	Primary SOC, HLGT, HLT and PT
	Primary SOC and PT
Treatment emergent SAE related to IMP as per Investigator's judgment	Primary SOC, HLGT, HLT and PT
TEAE leading to permanent intervention discontinuation	Primary SOC, HLGT, HLT and PT
	Primary SOC and PT
TEAE leading to death (death as an outcome of the AE as reported by the Investigator in the AE page)	Primary SOC, HLGT, HLT and PT

Type of AE	MedDRA levels
Pretreatment AE	Overview ^a
	Primary SOC and PT

^a Will include the following AE categories: any AEs, any serious AEs, any AEs leading to death, any AEs leading to permanent intervention discontinuation

Analysis of deaths

In addition to the analyses of deaths included in [Table 6](#) the number (%) of participants in the following categories will be provided:

- Deaths during the treatment-emergent and post-treatment periods
- Deaths in non-randomized or randomized but not treated participants.

Analysis of adverse events of special interest (AESIs) and other AEs of interest

Adverse events of special interest (AESIs) and other AEs of interest will be selected for analyses as indicated in [Table 8](#). Number (%) of participants experiencing at least one event will be provided for each event of interest. Tables will be sorted as indicated in [Table 6](#).

Table 8 - Selections for AESIs and other AEs of interest

AE Grouping	Criteria
AESI	

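### The secondary safety endpoint stops at Week 24, but the general TEAE and SAE tables run to last dose + 98 days, so no planned table reports the endpoint as worded

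*SAP*

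**What the plan says.** **Endpoint.** SAP 1.2 (Table 2) gives the secondary safety endpoint as the "Percentage of participants experiencing treatment-emergent adverse events (TEAEs) or serious adverse events (SAEs) from baseline through Week 24". Protocol 9.4.2 (Table 7) has the same endpoint: "Percentage of participants experiencing TEAEs or SAEs from baseline through Week 24".

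**Event window.** SAP 4.7.2 defines TEAEs as "AEs that developed, worsened or became serious during the treatment-emergent period". SAP 4.1 sets that period as "the period from the first IMP administration to the last IMP administration + 98 days". The shorter on-treatment period, "the period from the first IMP administration to the last administration of the IMP + 14 days", is also defined there, but SAP 4.7.2 does not use it to count adverse events. The summaries in SAP Table 7 "will be generated with number (%) of participants experiencing at least one event", and no onset limit at Week 24 is attached to them.

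**Events outside the window.** Protocol 9.4.2 says: "Serious AEs and AEs leading to study discontinuation that occur outside the treatment-emergent period will be summarized separately".

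**Data cut.** Protocol 1.1 and 9.6 and SAP 4.9 place the primary lock at the point when all randomized participants have finished the 24-week treatment phase. Follow-up data are added later and reported in an addendum. None of these sections defines a Week 24 cut for each participant.

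**Other Week 24 items.** These are the exploratory skin-infection endpoint (SAP 4.5) and optional Kaplan-Meier estimates for adverse events of special interest and selected groupings (SAP 4.7.2).

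**Exposure.** SAP 4.7.1 defines IMP exposure as last dose date minus first dose date plus 14 days. SAP 4.7.2 asks for rates per 100 patient-years, and for rates adjusted by exposure duration or by exposure duration at risk, without giving a formula for the person-time.

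**The concern.** An endpoint with a fixed time limit should be reported over that time. Here the percentage in the tables would cover a longer period for most participants. At the primary lock, the length of that period would also depend on when each person was randomized. A reader who takes the TEAE table as the Week 24 endpoint would read too high a percentage whenever events occur during follow-up.

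A lesser matter is that the exposure-adjusted rates, which the SAP version history says a health authority requested, have no defined denominator. Two programmers could produce different values from the same data.

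**Working it through.** **1. The windows.** Day number = 7 × week + 1, which agrees with the target days in SAP 5.4 (Week 24 = Day 169, Week 36 = Day 253). For safety, Day 1 is the first IMP administration (SAP 5.4). Dosing runs "from Week 0 until Week 22" (Protocol 1.3), so a completer's last dose is on Day 155.

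- Treatment-emergent period ends: 155 + 98 = Day 253, which is 252 days after first dose.
- Endpoint ends: Day 169, which is 168 days after first dose.
- Ratio: 252/168 = 1.5; difference 84 days.

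**2. Early stoppers.** The window closes before Day 169 when last dose + 98 < 169, that is, when the last dose is before Day 71.

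| Last dose | Day | Window closes |
|---|---|---|
| Week 8 | 57 | Day 155 |
| Week 10 | 71 | Day 169 |
| Week 22 | 155 | Day 253 |

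An event on, say, Day 160 in a Week 8 stopper is not a TEAE by the SAP's definition, so the TEAE part of the endpoint is not undercounted. The SAE part is open. The endpoint names SAEs through Week 24 without restricting them to the treatment-emergent period, while Protocol 9.4.2 sends such an SAE to a separate summary.

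**3. Size with full follow-up.** The documents give no adverse event rates, so these figures are illustrations. Let p be the true proportion by Day 169, and let k be the hazard after Week 24 relative to before. Over the full window the proportion is 1 − (1 − p)^((168 + 84k)/168). For p = 10%:

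- k = 1 (constant hazard): 1 − 0.9^1.5 = 14.6%
- k = 0.5: 1 − 0.9^1.25 = 12.3%
- k = 0: 10%

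In 75 participants, k = 1 means 11.0 rather than 7.5 with an event.

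**4. Size at the primary lock.** Assume completers only, constant hazard, uniform accrual over A days, and a calendar cut when the last participant reaches Week 24. Follow-up beyond Week 24 is then r = min(84, u), with u uniform on 0 to A. A share 84/A of participants has partial follow-up, with a mean proportion of 1 − (0.9 − 0.9^1.5)/(0.5 × ln(1/0.9)) = 12.33%. The rest have 14.62%.

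- A = 180: 0.467 × 12.33% + 0.533 × 14.62% = 13.6%
- A = 600: 0.140 × 12.33% + 0.860 × 14.62% = 14.3%

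**5. Between arms.** Both arms use the same rule, so the ratio moves only if early stopping differs. Take the same true 10% in both arms, constant hazard, full follow-up, and stopping at Week 8 in 5% of one arm and 25% of the other (assumed). A Week 8 stopper contributes 1 − 0.9^(154/168) = 9.2%. The arms show 0.95 × 14.6% + 0.05 × 9.2% = 14.3% and 0.75 × 14.6% + 0.25 × 9.2% = 13.3%. That is a gap of about 1 percentage point under a marked imbalance.

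**6. Person-time.** For a completer, the only defined exposure is 154 + 14 = 168 days, while events are counted over 154 + 98 = 252 days. If that exposure were used as the denominator, the last 84 days of the event window would be left out. For the event rate requested for adverse events of special interest and groupings, this overstates the rate by up to 252/168 = 1.5 times in completers under a constant hazard, and not at all if no later events occur.

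**The case against.** **The lock may already give the Week 24 result.** Protocol 1.1 and 9.6 and SAP 4.9 say that follow-up data are added after the primary lock and reported in an addendum. This can be read as 24 weeks in the main report and follow-up in the addendum, in which case the main tables would largely match the endpoint. The same sentences can also be read as a calendar cut. The documents do not settle it, so the doubt stands.

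**The protocol itself pairs the endpoint with these tables.** Protocol Table 7 puts the Week 24 wording beside ordinary TEAE incidence tables, and the SAP follows that method. This suggests loose wording rather than a forgotten analysis, and aligning the wording would also remove the conflict. It does not remove the need to do one or the other.

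**Stronger readings that the documents do not support.**

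- A reader might infer that every adverse event table has the wrong window. SAP Table 7 also includes pretreatment summaries, so the point concerns the general TEAE and SAE tables.
- A reader might infer that early stoppers' events are lost. Later events are not TEAEs, and SAEs outside the window are still reported, but separately.
- A reader might take 14.6% as the figure expected at the primary lock. That needs the full 84 days in everyone, which the last participants randomized cannot yet have.
- A reader might infer that the exposure-adjusted rates are wrong by a factor of 1.5. The denominator is undefined, not misstated, and that factor applies only to the event rate for adverse events of special interest and groupings, and only if the + 14-day exposure is used.

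**Conclusion.** The inconsistency holds. The endpoint ends at Week 24, no general TEAE or SAE table is limited to Week 24, and no per-participant Week 24 cut is stated. The day arithmetic rests only on the documents' own schedule.

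The size rests on assumptions about hazard and accrual that the documents cannot confirm. For a true 10%, the illustrations run from 10% (no later events) through 13.6% to 14.3% (primary lock) to a ceiling of 14.6% (full follow-up). SAP 4.7 makes safety descriptive with no testing, so the effect is on absolute percentages, not on type I error, power or the primary endpoint. The comparison between arms changes little. The change should be made because the plan otherwise does not report a secondary endpoint that it names. The person-time point is a minor clarification.

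**What to change.** 1. In SAP 4.7.2, add one TEAE/SAE table, n (%), in the safety population, limited to onset from first IMP through Day 169. State whether its SAE row includes SAEs that fall after the treatment-emergent period but before Day 169.
2. Keep the full treatment-emergent tables, and label each with its window and data cut.
3. In SAP 4.7.2, state that the person-time for each exposure-adjusted rate covers the same window as its counted events, with participant rates censored at first event.

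The cost is one extra table and a few lines of text, using data already collected. The Week 24 percentages will usually be lower than those in the full tables, which is why the labels matter. Rewording the endpoint to the treatment-emergent period would also resolve the conflict, but it changes a protocol endpoint.
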